### **9.3 Analysis of Laboratory Data**

Data collected from central and local laboratories, including additional laboratory testing due to an SAE, will be used in all analyses, except for Baseline where SAE-related laboratory assessments on or before the first dose of study drug will be excluded. The clinical laboratory tests defined in the protocol operations manual (i.e., hematology and clinical chemistry) will be summarized.

Each laboratory variable will be summarized for all time points (starting with Baseline) with the number of non-missing observations, mean and standard deviation, median, minimum and maximum. Mean change from baseline to each applicable post-baseline visit will be summarized for selected laboratory variables, with the number of observations, baseline mean, and visit mean. The change from baseline mean, standard error, and 95% confidence interval will be presented for the mean change from baseline.

Below are selected laboratory variables:

**Hematology**      Platelet count, hemoglobin, white blood cell (WBC) count, Lymphocytes, Neutrophils

**Chemistry**      Albumin, Alkaline Phosphatase, ALT, AST, Bilirubin, Creatinine, Glucose, Potassium, Magnesium, Sodium

Changes in selected laboratory parameters will be tabulated using shift tables by NCI CTC criteria and categorized as low, normal, or high based on the normal ranges of the laboratory used for each sample. A shift table from baseline either to the worse value (based on NCI CTC criteria) during treatment or to minimum and maximum value (based on normal range), will be created. A similar shift table will be provided to summarize shifts from baseline to the final post-baseline value.

In addition, the number and percentage of subjects who have potentially clinically significant (PCS) laboratory values meeting the following criteria any time during the appropriate Treatment Period will be summarized. Listings will be provided to summarize subject-level laboratory data for subjects meeting PCS criteria.

Analyte	PCS Low Threshold	PCS High Threshold
Hematocrit	$\leq 24\%$	$\geq 54\%$
Hemoglobin	$\leq 8.0 \text{ g/dL}$	$\geq 16 \text{ g/dL}$
Red Cell Count	$\leq 2.5 \times 10^6/\text{uL}$	$\geq 7.0 \times 10^6/\text{uL}$
MCV	$\leq 0.8 \times \text{LLN}$	$\geq 1.2 \times \text{ULN}$
MCH	$\leq 0.8 \times \text{LLN}$	$\geq 1.2 \times \text{ULN}$
MCHC	$\leq 0.8 \times \text{LLN}$	$\geq 1.2 \times \text{ULN}$
White Cell Count	$\leq 3 \times 10^3/\text{uL}$	$\geq 16 \times 10^3/\text{uL}$
Platelet Count	$\leq 100 \times 10^3/\text{uL}$	$\geq 800 \times 10^3/\text{uL}$
Neutrophils Absolute	$\leq 1.0 \times 10^3/\text{uL}$	$\geq 12.0 \times 10^3/\text{uL}$
Lymphocytes Absolute	2y – 4y: $\leq 1.0 \times 10^3/\text{uL}$ > 4y: $\leq 0.5 \times 10^3/\text{uL}$	> 2y-4y: $\geq 15 \times 10^3/\text{uL}$ > 4y: $\geq 10 \times 10^3/\text{uL}$
Monocytes Absolute	$\leq 0.1 \times 10^3/\text{uL}$	$\geq 3.0 \times 10^3/\text{uL}$
Eosinophils Absolute		$\geq 1.0 \times 10^3/\text{uL}$
Basophils Absolute		$\geq 0.6 \times 10^3/\text{uL}$
Albumin	$\leq 2.0 \text{ g/dL}$	$\geq 6.0 \text{ g/dL}$
Alkaline Phosphatase		$\geq 2 \times \text{ULN}$
ALT		$\geq 2 \times \text{ULN}$
AST		$\geq 2 \times \text{ULN}$
Bilirubin		$\geq 2 \times \text{ULN}$
Lactate Dehydrogenase		$\geq 2 \times \text{ULN}$
Creatinine	$\leq 0.3 \text{ mg/dL}$	$\geq 1.5 \text{ mg/dL}$ or increase by 0.3 mg/dL
Magnesium	$\leq 1.0 \text{ mg/dL}$	$\geq 3.5 \text{ mg/dL}$
Glucose	$\leq 50 \text{ mg/dL}$	$\geq 180 \text{ mg/dL}$
Chloride	$\leq 90 \text{ mEq/L}$	$\geq 115 \text{ mEq/L}$
Bicarbonate	$\leq 16 \text{ mEq/L}$	$\geq 35 \text{ mEq/L}$
Calcium	$\leq 7.0 \text{ mg/dL}$	$\geq 13.0 \text{ mg/dL}$
Potassium	$\leq 3.0 \text{ mEq/L}$	$\geq 6.0 \text{ mEq/L}$
Sodium	$\leq 130 \text{ mEq/L}$	$\geq 155 \text{ mEq/L}$

## 9.4 Analysis of Vital Signs and Weight

For blood pressure, respiratory rate, temperature, weight, BMI, and BMI SD score, the sample size, mean, standard deviation, median, minimum, and maximum will be

summarized. In addition, mean changes from baseline to each scheduled assessment will be summarized with the baseline mean, visit mean, change from baseline mean, standard deviation, and median.

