4.2 Discussion of Study Design

Choice of Control Group

For ethical reasons, this study does not have a placebo control group, as intervention in this patient population is essential, and treatment should start immediately to maximize possible benefits of GnRHa treatment. Also, for ethical reasons, this study does not have an active control group, as differences in dosing frequencies would require sham injections.

Appropriateness of Measurements

Standard statistical, clinical, and laboratory procedures will be used in this study. All efficacy measurements in this study are standard for assessing disease activity in subjects with CPP. All clinical and laboratory procedures in this study are standard and generally accepted.⁶

Suitability of Subject Population

Both treatment-naïve subjects and those who were previously treated with a GnRHa were selected for this study, as both populations may benefit from the proposed extended dosing interval either as initial therapy or maintenance therapy, respectively.

Selection of Doses in the Study

The LA 45 mg 6-month dose in this study was chosen to extend the dosing interval to reduce the number of injections. The formulation chosen for this study is the same as the approved Lupron Depot 45 mg 6-month dose for prostate cancer and contains 45 mg of LA in a prefilled dual chamber syringe. LA is the same active ingredient as in the approved Lupron Depot-PED 11.25 mg 3-month and 30 mg 3-month CPP formulations. The injection volume for the 45 mg 6-month dose is also the same as that in the approved 11.25 mg 3-month and 30 mg 3-month CPP formulations. The same prefilled, dual chamber syringes and needles are used for the 3-month and 6-month formulations.

The average monthly dose of LA with a 45 mg 6-month dose is expected to be 7.5 mg because of the sustained release characteristics of the 45-mg formulation. This is consistent with that of the lower dose, shorter-duration formulations. This monthly exposure to leuprolide is identical to the lowest Lupron Depot-PED dose that is approved in the US (7.5 mg 1-month formulation) and is half that of the highest approved Lupron Depot-PED dose (15 mg 1-month formulation).

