3.12 Vital Signs

Vital sign determinations of systolic and diastolic blood pressure, pulse rate, body temperature (rectal, oral, aural, or axillary), and respiratory rate will be obtained at the visits specified in Section 2.

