6.3 Method of Assigning Subjects to Treatment Groups

This is an open-label, nonrandomized, single-arm study. All subjects will receive the same dosage of LA (45 mg intramuscular every 24 weeks) for the duration of the study.

At the Screening Visit, all subjects will be assigned a unique subject number through the use of the IRT. For subjects who do not meet the study selection criteria, site personnel must contact the IRT system and identify the subject as a screen failure.

Subjects who are enrolled will retain their subject number assigned at the Screening Visit throughout the study. Upon receipt of study drug, the site will acknowledge receipt in the IRT system.

Contact information and user guidelines for IRT use will be provided to each site.

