#### **4.3.3 Other Efficacy Endpoints**

The following other efficacy endpoints will be summarized:

- Peak stimulated LH concentrations at each scheduled assessment (not already specified in Section 4.3.2).
- Number and percentage of subjects who fail suppression of peak stimulated LH per primary endpoint analysis at each scheduled assessment.
- Number and percentage of female subjects with menstrual bleeding.
- Change from baseline in basal and peak stimulated LH, FSH, as well as basal and stimulated estradiol (for females) and testosterone (for males), to each scheduled assessment.
- Ratio and change from baseline in the ratio of bone age to chronological age at each scheduled assessment.
- Regression or no progression in pubic hair in both females and males.
- Change from baseline in uterine length, uterine volume, and ovarian volume to each scheduled assessment.
- Number and percentage of subjects with endometrial stripe presence by baseline endometrial stripe presence status (yes/no) at each scheduled assessment.
- Change from baseline in testicular length (cm), penile length (cm), and penile width (cm) by physical examination, and in testicular volume by Prader beads to each scheduled assessment.
- Change from baseline in BMI standardized score to each scheduled assessment
- Change from baseline in height standardized score to each scheduled assessment
- PedsQL and PROMIS questionnaires at each scheduled assessment.

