### **9.0 Safety Analyses**

#### **9.1 General Considerations**

The Safety Analysis Set consists of all subjects who received at least 1 dose of study drug. All safety analyses will be performed by previous GnRHa status (naïve or previously treated), and overall.

The following summary statistics will be presented for subjects who have both baseline and post-baseline values for laboratory parameters and vital signs: the mean value at baseline and at each respective protocol specified visit, and the mean, standard deviation and median for changes from Baseline. Categorical data will be summarized using frequencies and percentages.

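### SAP 9.4 summarises blood pressure only as raw change in growing children, so late (Part 2) mean changes mix growth with any drug effect; its list also omits pulse rate

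*SAP*

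**What the plan says.** SAP 9.4 names the variables to be tabulated: "For blood pressure, respiratory rate, temperature, weight, BMI, and BMI SD score". It plans the usual descriptive statistics, including minimum and maximum, and says that "mean changes from baseline to each scheduled assessment will be summarized". Blood pressure gets no reference to age, sex or height.

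Operations Manual 3.12 lists what is measured: "systolic and diastolic blood pressure, pulse rate, body temperature (rectal, oral, aural, or axillary), and respiratory rate". Pulse rate is the only one of these that SAP 9.4 does not name. SAP 9.1 has a broader rule, with baseline, visit and change summaries "for subjects who have both baseline and post-baseline values for laboratory parameters and vital signs", but it names no individual vital sign.

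SAP 4.3.4 makes vital signs a safety endpoint for the whole study. Children enter at ages 2 to 11, depending on sex and previous treatment (Protocol 5.1, criteria 17 and 20), and are treated for up to 144 weeks (Operations Manual 5.2). On design, Operations Manual 6.3 says: "This is an open-label, nonrandomized, single-arm study".

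**The concern.** Blood pressure can be expected to rise as children grow. Over a short treatment period the rise is small, but over nearly three years it may not be. With no concurrent comparison, a raw mean change at Week 120 or 144 is the sum of growth and any effect of the drug, and the planned table cannot divide the two. A rise due to growth could be taken for a drug effect, or a modest drug effect could be dismissed as growth.

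Other planned safety outputs would not readily pick up a gradual shift. Under Protocol 6.1 a vital-sign change becomes an adverse event only if it leads to discontinuation or therapeutic intervention, or if the investigator judges it to be one. SAP 9.3 gives laboratory values shift tables and thresholds for potentially clinically significant results; SAP 9.4 gives vital signs neither. Minimum and maximum are raw and pooled over a wide age range, so a reading that is high for a small child need not stand out.

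The pulse-rate gap is simpler. SAP 9.4 is where the variables are named, and a programmer working from it would have no instruction to tabulate pulse.

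**Working it through.** **The plan's own figure.** None is given for vital signs. The only precision figure, 16.7% in SAP 4.4, concerns the LH response rate. It reproduces as the largest distance from an observed rate to an exact Clopper-Pearson 95% limit with n = 40 (0.16699, at 25 of 40). Only N = 40 is used below.

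**Inputs from the documents.** N = 40; visits at Weeks 48, 72, 96, 120 and 144; at least 15 children in each previous-treatment group.

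**Assumptions, not in the documents.** Growth-only rise in blood pressure of 1 to 2 mmHg per year, with 0.5 and 3 as outer values. SD of individual change of 8, 10 or 12 mmHg.

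**Step 1: time on study.** Years = weeks × 7 / 365.25. Week 48 is 0.92 years and Week 144 is 2.76 years.

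**Step 2: growth-only mean change.** Rate × years, in mmHg:

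| Visit | Years | 0.5/year | 1/year | 2/year | 3/year |
|---|---|---|---|---|---|
| Week 48 | 0.92 | 0.5 | 0.9 | 1.8 | 2.8 |
| Week 72 | 1.38 | 0.7 | 1.4 | 2.8 | 4.1 |
| Week 96 | 1.84 | 0.9 | 1.8 | 3.7 | 5.5 |
| Week 120 | 2.30 | 1.1 | 2.3 | 4.6 | 6.9 |
| Week 144 | 2.76 | 1.4 | 2.8 | 5.5 | 8.3 |

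**Step 3: sampling error of a mean change.** 95% half-width = 1.96 × SD / √40. SD 8 gives 2.48, SD 10 gives 3.10 and SD 12 gives 3.72 mmHg. SAP 9.4 plans no such interval; it serves here only as a yardstick.

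**Step 4: comparison.** At Week 48 the drift of 0.9 to 1.8 mmHg is below all three half-widths. At Week 144 a drift of 5.5 mmHg (2 per year) exceeds all three, while 2.8 mmHg (1 per year) exceeds only the SD 8 value. Drift at Week 144 equals the half-width at 2.48/2.76 = 0.90, 3.10/2.76 = 1.12 or 3.72/2.76 = 1.35 mmHg per year, for SD 8, 10 and 12 respectively. At 0.5 per year it never reaches the half-width.

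**Step 5: by previous treatment.** SAP 9.1 also asks for safety results by previous-treatment group. With 15 children the half-widths are 1.96 × SD / √15 = 4.05, 5.06 and 6.07 mmHg, so growth is harder to see in a group of that size. Discontinuations before Week 144 would widen all of these figures. They would not reduce the drift, which is a bias and does not shrink or grow with N.

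**Step 6: pulse rate, texts side by side.** Operations Manual 3.12 has systolic and diastolic pressure, pulse, temperature and respiratory rate. SAP 9.4 has blood pressure, respiratory rate and temperature, plus weight and two BMI measures. Pulse is the one vital sign unmatched.

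**The case against.** The strongest reply is that the size rests on assumed rates. That is correct: the documents give neither a drift nor an SD, and at the low end of the range growth stays within sampling error throughout. It is also correct that the Part 1 analysis at Week 48 is barely affected. The point is confined to the later visits.

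A second reply is that nothing is lost, because date of birth, sex and height are collected and the scores could be derived at any time. That stands, and it is also why the change is cheap to specify in advance. It can be added that no blood pressure or heart-rate event is among the adverse events of special interest, so the plan signals no particular worry here.

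Several stronger readings are tempting, and the documents do not support them:

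- A reader might infer that vital-sign safety cannot be interpreted at all. Respiratory rate and temperature are summarised, extremes are shown, adverse events are collected, and early visits carry little drift.
- A reader might extend the point to weight. SAP 9.4 puts BMI SD score beside raw weight, and SAP 4.3.3 adds a standardised BMI score and "Change from baseline in height standardized score to each scheduled assessment", so body size already has growth-referenced measures.
- A reader might fault the missing control arm. Protocol 4.2 discloses and explains it: "For ethical reasons, this study does not have a placebo control group". It is the reason an external reference helps, and not a defect of SAP 9.4.
- A reader might conclude that pulse will go unreported. SAP 9.1 covers vital signs as a class, and the Operations Manual counts pulse among them, so the gap is an inconsistency between sections.

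**Conclusion.** The point holds in a limited form. SAP 9.4 gives blood pressure no growth reference, so mean change at the late Part 2 visits cannot be separated from growth. If growth adds 1 to 2 mmHg per year and the SD of change is 8 to 12 mmHg, the growth component at Week 144 is 2.8 to 5.5 mmHg against a half-width of 2.5 to 3.7 mmHg for 40 children. It is therefore comparable with sampling error or larger. At Week 48 it is within it. Above about 1.35 mmHg per year it exceeds sampling error at Week 144 for every SD considered. All of this depends on the assumed rates and on 40 children still contributing at Week 144.

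The pulse-rate omission is a list to be reconciled and would not on its own amount to more than that. Overall this is a minor matter of safety reporting. It does not affect the sample size, the primary analysis or the conduct of the study.

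**What to change.** In SAP 9.4:

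1. Add systolic and diastolic blood pressure scores referenced to age, sex and height, with change from baseline at each scheduled assessment, beside the raw values. Name the reference used; the SAP names none for its BMI and height scores, so there is nothing to carry over.
2. Add pulse rate to the list, so that 9.4 agrees with SAP 9.1 and Operations Manual 3.12.

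The cost is one reference to cite and a few derived variables. Date of birth, sex and height are already recorded (Operations Manual 3.3 and 3.11), so no new data are needed. One limit should be stated with the results: such a score removes the change expected in the reference population, which may not be exactly the change expected in treated children with central precocious puberty. It narrows the ambiguity without closing it. The change should be made before the end-of-Part-2 analysis, where it matters most.

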## **10.0      Summary of Changes**

### **10.1      Summary of Changes Between the Previous Version and the Current Version**

Remove the laboratory values in Section [9.3](#) that are not supported by CTCAE criteria 4.03.

### **10.2      Summary of Changes in Previous Version**

Summary of changes between the second version and the third version include:

- Section [4.9](#) Missing Data Imputation has been updated for the endpoint of suppression of GnRHa-stimulated LH. Subjects who received study drug at Day 1 visit and are missing results in Part 1 will be considered as LH suppression failures.
- Addition of Subgroup Analysis in Section [5.2](#)
- Addition of Study Drug Duration in Section [6.0](#)
- Addition of Section [7.0](#) for analyses for demographics, baseline characteristics, medical history, and prior/concomitant medications
- Section [9.2.1.1](#) Adverse Event Overview has been updated to include AE related to COVID-19 and deaths occurring  $\leq$  or  $>$  36 weeks after last dose of study drug
- Section [9.2.1.4](#) Adverse Events by Maximum Relationship has been updated to change "Possibly or Definitely related" to "Reasonable Possibility" to align with eCRF.
- Section [9.2.1.7](#) Hormonal Flare Response Adverse Events has been updated to add a description of analysis for hormonal flare response adverse event and to update the definition of biochemical AOC phenomenon
- Section [9.3](#) Analysis of Laboratory Data has been updated with more details
- Addition of [Appendix A](#) for definition of AESI

Summary of changes between the initial and second version includes the following:

The primary, secondary and other efficacy endpoints have been updated to reflect changes in protocol. The primary efficacy endpoint has been changed to the proportion of subjects with suppression of GnRHa-stimulated LH (< 4 mIU/mL) at Week 24 after the first dose of study drug. The secondary and other efficacy endpoints have been updated in Section 4.3.2 and Section 4.3.3. The analysis for the primary efficacy endpoint has been changed to two-sided 95% confidence interval based on the binomial distribution (Clopper-Pearson exact method).

## **Appendix A. Definition of Adverse Events of Special Interest (AESI)**

Adverse Events of Special Interest (AESI) will be identified using the following search criteria:

Item of Safety Interest	Method of Surveillance
Bone fracture	Bone fractures CMQ
Slipped capital femoral epiphysis	Fractures HLGT and Epiphyseal disorders HLT (limit to under 18 years of age)
Neuropsychiatric events	Suicide/self-injury SMQ_Narrow
Seizure/convulsion	Convulsions SMQ_Broad
Injection site reaction	Injection site reaction CMQ
Hypersensitivity reactions	Hypersensitivity SMQ Narrow

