- 12. No history of clinically significant medical conditions or any other reason that the investigator determines would **interfere with the subject's participation** in this study or would make the subject an unsuitable candidate to receive study drug.
- 13. No history of an **allergic reaction** or significant sensitivity to constituents of the study drug (and its excipients) and/or other products in the same class.

Pregnancy

- 14. A **negative serum pregnancy test** for female subjects \geq 10 years of age at Screening and negative urine pregnancy test on Day 1 prior to study drug administration. For female subjects $<$ 10 years of age, pregnancy tests may be performed at Screening and on Day 1 at the discretion of the principal investigator.

Concomitant Medications

- 15. Must have discontinued therapy with medroxyprogesterone acetate, growth hormone, insulin-like growth factor-1 (IGF-1), or estrogen or testosterone preparations at least 5 half-lives or 4 weeks prior to Screening, whichever is longer.
- 16. Must not have been treated with **any investigational drug** within 30 days or 5 half-lives of the drug (whichever is longer) prior to Screening or is currently enrolled in another clinical study.

Additional Criteria for Subjects Naïve to GnRHa treatment

- 17. Females 2 – 8 years of age, inclusive, or males 2 – 9 years, inclusive, on Day 1.
- 18. Pretreatment pubertal response to GnRHa stimulation test ($LH \geq 6$ mIU/mL) at Screening.
- 19. Breast pubertal staging (modified Tanner) of at least 2 in females; testicular volume of at least 4 cc in males at Screening.

Additional Criteria for Subjects Previously Treated with a GnRHa

- 20. Females 2 – 10 years of age, inclusive, or males 2 – 11 years of age, inclusive, on Day 1.
- 21. Must have been on GnRHa therapy for at least 6 months prior to Day 1.
- 22. Should have documented maintenance of LH suppression as evidenced by peak stimulated $LH < 4$ mIU/mL at Screening.

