3.19 Administration of Study Drug

Study drug will be administered to subjects beginning at Baseline (Day 1) and at the time points specified in Section 2 as follows:

Part 1: LA 45 mg 6-month, given as a single intramuscular injection. The first injection will be administered on Day 1, and the second injection will be administered at Week 24.

For subjects who were previously treated with GnRHa therapy, the first injection of study drug should be administered at the end of the previous GnRHa treatment cycle.

Part 2: LA 45 mg 6-month, given as a single intramuscular injection at 24-week intervals (up to 24 months) starting at Week 48 until Week 120.

Study site staff will administer all injections of LA 45 mg 6-month. Each injection of study drug should be administered in the gluteal area, anterior thigh, or deltoid. Injection sites should be alternated to minimize injection site reactions.

If a subject cannot come to the site because of unforeseen circumstances (e.g., the COVID-19 pandemic), the injection of study drug may be administered by a home healthcare nurse at the subject's home. AbbVie should be notified if this occurs.

Refer to Section 7.3 for dose preparation instructions.

Depending on local regulations, provisioning of study drug and generic LA for stimulation test for direct-to-patient (DTP) and direct-from-patient (DFP) transfer because of unforeseen circumstances (e.g., the COVID-19 pandemic) will be available upon request. AbbVie should be notified if this occurs. Sites can use Marken, a third-party vendor with which AbbVie has an agreement, for drug shipment in these circumstances or sites may use a local courier.

Sites will be responsible for meeting IRB reporting requirements and submitting the booking form (which will be provided) to the local IRB (as applicable).

The investigator must discuss the DTP process with the subject's parent or legal guardian:

- Obtain consent to provide delivery information to Marken and/or local courier and record this in source documentation.
- Obtain and review results of required safety procedures as applicable before registering subject dispensation of study drug in interactive response technology (IRT).
- Confirm that the subject's parent or legal guardian will be available to accept delivery.
- The site will follow-up with the subject's parent or legal guardian after shipment is received.

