#### **4.2.1 Study Design and Design Diagram**

The total duration of the study (Parts 1 and 2) will be 160 weeks as follows:

- Part 1: 52 weeks (4-week screening period + 48-week treatment period)
- Part 2: 108 weeks (additional 96-week treatment period + 12-week follow-up period)

**Part 1:** The safety, efficacy, pharmacokinetics, and pharmacodynamics of the LA 45 mg 6-month dose will be evaluated in subjects with CPP from Baseline to Week 48. In all subjects, blood samples for efficacy assessments (analysis of LH, testosterone concentrations [males], and estradiol concentrations [females]) will be collected at Baseline and at Weeks 1, 4, 12, 20, 24, 44, and 48 after dosing. In the first subjects who are enrolled (20 subjects total, with at least 8 naïve and 8 previously treated), concentrations of leuprolide will be measured at each study visit following administration of LA 45 mg 6-month to characterize the leuprolide concentration-time profile, rate of absorption, and pharmacokinetic/pharmacodynamic relationship of leuprolide and LH. Investigative sites will be notified when the pharmacokinetic subset has been fulfilled.

[figure not shown]
Leuprolide and appropriate measures of efficacy (LH, estradiol in females, testosterone in males) will be monitored upon data availability to evaluate the appropriateness of the 24-week dosing interval for the 6-month formulation for CPP.

**Part 2:** Following completion of Part 1 (the initial 48-week treatment period) assessments, subjects will continue to Part 2 of the study (extension period) to evaluate long-term administration of LA 45 mg 6-month (up to 24 months). Study visits during the extension period will start at Week 48 and continue once every 24 weeks for 96 weeks (24 months) until the subject discontinues treatment of LA 45 mg 6-month or withdraws from the study. Subjects will be assessed for continued maintenance of LH suppression and safety throughout this extension period.

A schematic of the study is shown in [Figure 1](#).

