### **9.2.1.6 Adverse Events of Special Interest**

Adverse events of special interest will be summarized by SOC and PT and will be based on standardized or company MedDRA queries (SMQs or CMQs), or based on adjudication results.

The following Adverse Events of Special Interest (AESI) will be summarized:

- Bone fracture
- Slipped capital femoral epiphysis
- Neuropsychiatric events
- Seizure/convulsion
- Injection site reaction
- Hypersensitivity reactions

Detailed information about the search criteria is provided in [Appendix A](#).

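### The SAP Appendix A search for slipped capital femoral epiphysis does not isolate that event: its age limit removes nobody and, read as a union, it takes in every ordinary fracture

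*SAP*

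**What the plan says.** SAP Appendix A is the operative definition. It states that "Adverse Events of Special Interest (AESI) will be identified using the following search criteria", followed by one row per event. The row for slipped capital femoral epiphysis reads "Fractures HLGT and Epiphyseal disorders HLT (limit to under 18 years of age"). It gives no anatomical site, no list of preferred terms, no exclusion of other fractures and no review step. The row for bone fracture is separate and uses its own company query, "Bone fractures CMQ".

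SAP 9.2.1.6 lists "Slipped capital femoral epiphysis" as an AESI distinct from bone fracture. Protocol 6.1 and Operations Manual 4.1 also keep it apart from their item on fracture, osteoporosis and osteopenia. SAP 9.2.1.6 has AESIs tabulated by system organ class (SOC) and preferred term (PT). It says they rest on MedDRA queries or on adjudication results. Neither document describes an adjudication process or assigns one to this event.

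**The concern.** The row combines two MedDRA groupings, and its only stated restriction is age. In a database that mixes adults and children an under-18 limit would narrow the search. In a trial that enrols only young children it may narrow nothing, and the whole fracture grouping would then count towards a category named for one specific hip event.

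Safety is part of the primary objective, and the study has a single arm, so no concurrent control would show that such a count is only background. A category that mixes ordinary childhood fractures with slipped epiphysis does not report the risk it names. The word 'and' adds a second problem: two programmers could implement it differently and obtain different counts.

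**Working it through.** The plan states no figure for this category, so there is none to reproduce. There are three checks.

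**1. Does the age limit exclude anyone?**

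Inputs:
- Entry ages, Protocol 5.1: previously treated, "Females 2 – 10 years of age, inclusive, or males 2 – 11 years of age, inclusive, on Day 1"; naïve, "Females 2 – 8 years of age, inclusive, or males 2 – 9 years, inclusive, on Day 1". An inclusive upper age of 11 means under 12.
- Last injection, Operations Manual 3.19: "at 24-week intervals (up to 24 months) starting at Week 48 until Week 120".
- Adverse-event window, SAP 9.2.1: 24 weeks of drug effect plus 12 weeks after the last dose, so 120 + 24 + 12 = Week 156. This agrees with the 160-week total in SAP 4.2.1 less 4 weeks of screening.
- Visit windows, Operations Manual 2.2 and 2.3: ± 6 days at Week 120 and ± 6 days at the follow-up call, so 12 days at most.

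Formula: highest age = upper entry age + 156 × 7 / 365.25 = upper entry age + 2.99 years.

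| Group | Day 1, under | Week 156, under | With 12 days added, under |
|---|---|---|---|
| Naïve girls | 9 | 11.99 | 12.02 |
| Naïve boys | 10 | 12.99 | 13.02 |
| Previously treated girls | 11 | 13.99 | 14.02 |
| Previously treated boys | 12 | 14.99 | 15.02 |

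A boy entering just under 12 would need 6 × 365.25 / 7 = 313 weeks to reach 18, about twice the 156 available. The limit excludes no eligible child, whether the parenthesis applies to both groupings or only to the second.

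**2. What does each reading of 'and' count?**

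- *Union* (a list of groupings to search, the usual convention): all terms under Fractures plus all terms under Epiphyseal disorders. A case coded to an epiphyseal term is captured, and so is every ordinary fracture.
- *Intersection*: only terms lying in both groupings. Fractures outside the epiphyseal grouping are not counted, and neither are epiphyseal terms outside the fracture grouping. Which terms those are depends on the MedDRA hierarchy, which the documents do not contain.

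The SAP does not say which applies.

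**3. How large could the fracture contribution be under the union?**

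The documents give no fracture rate, so p below is an assumed risk per child over the whole study. It is applied to the planned 40 subjects, with all followed and children independent. Expected number = 40p; chance of at least one = 1 − (1 − p)^40.

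| Assumed p | Expected children in category | Chance of at least one |
|---|---|---|
| 1% | 0.4 | 0.331 |
| 2% | 0.8 | 0.554 |
| 5% | 2.0 | 0.871 |
| 10% | 4.0 | 0.985 |

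With a search restricted to epiphyseal terms, ordinary fractures would contribute 0 at every p.

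**The case against.** The strongest defence is the tabulation. Under SAP 9.2.1.6 a wrist fracture appears on its own PT line and an epiphyseal event on another. With about 40 children and few events, a careful reader could separate them. The SAP also does not state that a total for the slipped-epiphysis category will be displayed; the only AESI total it specifies is the any-AESI row in SAP 9.2.1.1. This stands as a limit on the harm. It does not make the category count correct, because Appendix A defines the AESI by the search.

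A second defence is that Appendix A heads its column as a method of surveillance, which suits a deliberately wide net for a rare event, and that SAP 9.2.1.6 mentions adjudication. A wide net is reasonable for retrieving candidates. But the appendix is titled as a definition, and no step turns retrieved hits into counted cases.

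Some stronger inferences are not supported:
- *That the search misses slipped epiphysis on either reading.* The union includes the epiphyseal grouping and can capture a true case; it fails to isolate one.
- *That a true case would be hidden, or that a false signal would pass unnoticed.* The PT lines make either hard to sustain.
- *That fractures are certainly counted in both bone categories.* This is likely, but the contents of the company fracture query are not given.
- *That the any-AESI row is inflated.* It is unchanged if the same fracture already counts under bone fracture.

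**Conclusion.** The row is wrong as written, with modest consequence. It is certain, for eligible children, that the age limit is inert. On the union reading it also follows that ordinary fractures fall in the slipped-epiphysis category, so the category does not isolate an event that both documents list separately from fracture. On the intersection reading the count would differ, and leaving the choice open is itself a defect in a definition.

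The size is illustrative only: 0.4 to 4 of 40 children expected from fractures alone for an assumed 1% to 10% risk per child, given the union reading and complete follow-up. This is descriptive safety reporting. The primary efficacy result is untouched, and the any-AESI row may not change. The row should be corrected, but it does not threaten the trial's main conclusion.

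**What to change.** In SAP Appendix A, revise the slipped capital femoral epiphysis row:

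- Delete the under-18 limit.
- Count as slipped capital femoral epiphysis only events in the Epiphyseal disorders HLT, or events under named preferred terms for that condition. Leave other fractures to the bone fracture row.
- If the Fractures HLGT is kept, label it a screen only. The sponsor's medical reviewer checks fracture verbatim terms for femoral epiphyseal events before database lock, and only confirmed hits are counted.

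The cost is one edited row, a re-run search and review of a handful of events. Narrowing the automatic search loses a little sensitivity for a case coded only as a fracture; the verbatim check covers that.
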